6.3.3. Secondary analyses

Pilot Study

In the pilot study, secondary analyses will examine group differences, including at-risk versus no-risk participants, gender comparisons, and subtype comparisons among at-risk adolescents, based on PUI symptoms and burden. These analyses will employ multiple-hierarchical (moderated) regression models to explore interactions between predictor and moderator variables in predicting PUI symptoms and clinical outcomes (including burden) at T1.

Structural equation modelling (SEM), covering both manifest and latent variables, will assess relationships and interactions between PUI symptoms, clinical variables, and moderating/mediating factors (T0+3 assessment). The SEM will align with the Bootstrap logic model (Figure 4).

Randomised Control Trial

For the RCT, each factor (allocation method, intervention) will be analysed separately. The same analytical approach as the pilot study will be used, focusing on group differences (at-risk vs. no-risk, gender, subtypes of at-risk adolescents) through multiple-hierarchical regression analyses at T2.

SEM will also be applied to explore symptom interactions and moderating/mediating variables (T0+3 assessment), following the BOOTSTRAP logic model.

Missing data will be assessed for potential estimation bias. If data are missing at random (MAR), multiple imputation will be used. Where missingness is linked to specific demographic or psychological variables, alternative sensitivity analyses will be considered.

Additionally, a health economic analysis within the BootStRaP project will assess both the cost and burden of PUI among adolescents and evaluate the cost-effectiveness and cost-utility of the Emotional regulation intervention and Inhibitory control intervention. These analyses will focus on optimal intervention delivery using the developed risk algorithms.

The economic evaluation will be conducted from both mental health and societal perspectives, considering direct and indirect costs. From a mental health perspective, costs will include expenditures credited to the mental health care budget, aligning with the decision-maker's viewpoint. The societal perspective will encompass direct mental health care costs as well as indirect costs, such as productivity

losses and broader economic impacts. The analysis will incorporate discounting methods for the time horizon used, ensuring a comprehensive view of long-term costs and benefits.

To account for missing data, we will apply multiple imputation techniques, maintaining data integrity and robustness in the economic analysis. Both intent-to-treat and complete case analyses will be conducted, complemented by probabilistic sensitivity analysis to account for variability in economic inputs and costs across different study sites.

A key component of the health economic analysis will be the measurement of Health-Related Quality of Life (HRQoL). We will use two validated scales to provide a balanced assessment of mental health impacts:

- The Paediatric Quality of Life Enjoyment and Satisfaction Questionnaire (PQ-LES-Q) (Endicott et al., 2006) will serve as the primary utility scale. This instrument is particularly suitable for adolescents, as it captures relevant domains and is sensitive to the factors most likely influenced by PUI interventions.
- The EQ-5D-Y (Wille et al., 2010) will be included as a secondary outcome measure. This short (2-minute) and user-friendly tool offers a visual analogue version, which enhances its applicability in diverse settings.

Using both HRQoL measures will enable us to address content validity concerns with existing instruments, especially given that many available quality of life scales favour physical health outcomes over mental health. By leveraging BootStRaP's large, cross-country sample size, we aim to enhance the validity and generalizability of our findings across European contexts.

The economic outcomes will be expressed in terms of societal costs, converted to Quality-Adjusted Life Years (QALYs). We will present the costs of interventions through two primary metrics: incremental costs per QALY gained and incremental costs per adolescent with PUI in full remission. These metrics will provide clear insights into the value for money of the BootStrApp interventions, supporting evidence-based decision-making for policy and practice.

Additionally, we will perform an impact analysis, comparing our effectiveness and cost-effectiveness data with similar disorders where evidence-based interventions are routinely implemented. This benchmarking exercise will include Obsessive-Compulsive Disorder (OCD) (Osborne et al., 2019) and Gambling Disorder (Diaz-Sanahuja et al., 2021), using up-to-date evidence available at the time of analysis. Given the similarities in intervention type, low cost, and scalability of the screening and treatment approaches, we hypothesise a moderate cost-effectiveness ratio for the BootstrApp intervention.

By adopting this comprehensive health economic approach, the BootStRaP project aims to not only demonstrate the clinical effectiveness of its digital interventions but also provide robust economic evidence to support their widespread adoption and sustainability in real-world settings.

7. Ethical Considerations

The BootStRaP study will follow ICH Good Clinical Practice (GCP) principles and all relevant ethics and governance procedures, including HRA approvals. The Project Office (PO) at UoH will provide GCP and GDPR-compliant governance documents, supported by legal and regulatory expertise to ensure alignment with EU standards. An independent Ethics Advisory Board will oversee the project.

The PO, in collaboration with local teams, will supply standardised study materials (e.g. protocol, plain-language information sheets), which can be adapted for local ethics submissions. All documents will be securely stored in the Trial Master File.

No site will begin recruitment until PO approval and site initiation are complete. The study database will remain inaccessible until all documentation is in place, with final sign-off by the Chief Investigator (CI).

The BootStRaP team will submit biannual progress reports and a midterm recruitment report to Horizon Europe. Local reporting and end-of-study declarations will follow national regulations, typically within 90 days of study completion.

8. Quality Assurance and Control

Quality Assurance (QA) involves all planned and systematic actions implemented to ensure that the trial is conducted, and data is generated, documented, recorded, and reported in accordance with Good Clinical Practice (GCP) principles and applicable regulatory requirements. Quality Control (QC) refers to the operational techniques and activities carried out within the QA system to verify that the quality standards for trial-related activities are consistently met.

The UoH Quality Management System (QMS) will be adapted to develop study-specific documents covering study setup, site initiation, ethical management, participant safety, quality management, and data monitoring and integrity. While data management will be led by the Data Management group consisting of members from UZL, IDC, UoH and the Project Office.

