Study Objective(s)	
The aim of this phase of the study, which incorporates both a pilot study (cohort 2) and an RCT (cohort 3), is to investigate two promising theory-informed candidate preventative interventions, targeting A: emotional regulation and B: inhibitory control, for Problematic Use of the Internet (PUI).
 
For the Pilot study: The primary objective is to use participants' individual characteristics to build models for predicting that predict outcomes for both novel preventative interventions when compared to a control condition (non-interactive provision of information on PUI).
 
The secondary objective is to explore the effectiveness of each preventative intervention compared to a control condition when allocated at random.
 
For the RCT: The primary objective is to evaluate the effectiveness of the predictive models derived from the pilot. We achieve this by comparing the effectiveness of each intervention (i.e., targeting emotional regulation or inhibitory control) when allocated either according to an algorithm derived from individual baseline outcome predictors (tailored arm), or when allocated at random (random arm) versus a control condition (non-interactive provision of information on PUI).
 
The secondary objective is to evaluate and compare the cost-effectiveness and cost utility of both allocation methods (tailored, random), investigating feasibility for large-scale implementation.

Planned Sample Size	3,600 (approximately 400 young people at each site), per cohort.
Participants	Young adolescents aged 12-16

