2.1. Study objectives

The second phase of the BootStRaP project aims to evaluate two promising, theory-informed preventative interventions for Problematic Usage of the Internet (PUI). This phase consists of a pilot study and a randomised controlled trial (RCT), designed to refine intervention strategies and optimise participant allocation.

Pilot Study

The primary objective of the pilot study is to identify key predictive characteristics that determine individual responses to the two interventions (emotional regulation and inhibitory control), compared to a control condition (non-interactive provision of psychoeducation on safe and effective use of the internet).

The secondary objective is to assess the overall effectiveness of each intervention relative to the control group under random allocation.

We do not expect one intervention to be superior to the other; rather, both are anticipated to be more effective than the control condition in reducing PUI risk. However, the primary focus is not on comparative effectiveness but on developing algorithms for personalised intervention matching, which will be applied in the subsequent RCT.

Randomised Control Trial

The primary objective of the RCT is to determine whether tailored intervention allocation (matching participants to either the emotional regulation intervention or inhibitory control intervention, using machine learning algorithms developed in the pilot study) leads to better outcomes compared to random allocation to the emotional regulation intervention or inhibitory control intervention or the control arm.

The secondary objective is to evaluate the cost-effectiveness and cost utility of this tailored approach, ensuring feasibility for large-scale implementation.

This structured approach will provide crucial insights into optimising individualised intervention strategies for preventing PUI in adolescents.

3. Methods

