4.5. Randomisation

In both the pilot and RCT studies, randomisation will be carried out using individualised, server-based assignment, based on each participant's access code at registration.

Pilot study: For the pilot study each participant will have an equal probability (33.3%) of being allocated to one of the three groups: Emotional regulation intervention group, Inhibitory control intervention group, or the control group.

RCT: For the RCT, each participant will have an equal probability (33.3%) of being allocated to one of three arms: tailored allocation, random allocation, control. This means that participants will have a 66.6% chance of allocation to an active intervention and 33% chance of allocation to the control arm.

Participants allocated to the random allocation arm will have a 50% chance of receiving the emotional regulation or inhibitory control intervention.

In the tailored allocation arm, participants will receive the intervention (targeting emotional regulation or inhibitory control) predicted as most likely to be effective for them by comparing their baseline profile (against the profile of response-predictors developed during the pilot study).

For both the pilot study and the RCT, both participants and researchers will remain blinded to the group allocation to minimise bias. The statistical analysis will be completed on blinded data (allocation A, B or C), with the blinding only being broken when the primary analysis has been completed.

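### The RCT's economic objective concerns tailored versus random allocation, but section 6.3.3 evaluates the two interventions and names no comparator

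*Protocol*

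**What the plan says.** **The objective.** The Study Summary says the RCT's secondary objective is to "evaluate and compare the cost-effectiveness and cost utility of both allocation methods (tailored, random". Section 2.1 says it is to "evaluate the cost-effectiveness and cost utility of this tailored approach" and does not say what tailoring is to be compared with. Neither place gives the RCT any other secondary objective.

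**The analysis.** Section 6.3.3, under its Randomised Control Trial heading, says the health economic work will evaluate the "cost-effectiveness and cost-utility of the Emotional regulation intervention and Inhibitory control intervention". The next sentence adds: "These analyses will focus on optimal intervention delivery using the developed risk algorithms". Results are to be presented as "incremental costs per QALY gained and incremental costs per adolescent with PUI in full remission", with no comparator stated.

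**How participants come to an intervention.** Section 4.5 randomises with equal probability to tailored, random and control. In the tailored arm, "participants will receive the intervention (targeting emotional regulation or inhibitory control) predicted as most likely to be effective for them", judged from the baseline profile. For the other active arm: "Participants allocated to the random allocation arm will have a 50% chance of receiving the emotional regulation or inhibitory control intervention".

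**The concern.** The objective asks whether a way of allocating is worth its cost. The analysis text asks about the value of two intervention contents. A cost per QALY for each intervention does not by itself say whether tailoring gives better value than random assignment.

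The two questions also rest on different data. Allocation method is randomised across whole arms. Intervention content is randomised in only one of the two active arms. In the other it follows from baseline predictors chosen because they are thought to relate to outcome. An economic result by intervention that pools both active arms would lose the protection of randomisation for the tailored half, whether the interventions are set against each other or each against control.

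At stake is whether the trial reports an economic result that matches its stated secondary objective and rests on its randomisation.

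**Working it through.** The main check is textual. The arithmetic only shows how much of the RCT is randomised to each contrast.

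**Step 1. The statements side by side.**

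| Place in Protocol | What is evaluated | Comparator |
|---|---|---|
| Study Summary, Study Objective(s) | Allocation methods | Tailored and random, compared |
| 2.1, Randomised Control Trial | Tailored approach | None named |
| 6.3.3, economic sentence | The two interventions | None named |
| 6.3.3, following sentence | Delivery guided by algorithms | None named |
| 6.3.3, incremental ratios | Cost per QALY and cost per remission | None named |

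No economic text in 6.3.3 states a tailored v random contrast. An incremental ratio has no meaning until its comparator is fixed, so the gap affects what is estimated.

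**Step 2. Reproduce the RCT sample size (section 3.4.2).** Inputs: d = 0.3, α = 0.05 (two-sided assumed), power 0.8, 70% completion, 30% at risk.
- Two-sample t-test: 175.4, rounded up to 176 per group. This agrees with the Protocol.
- Recruited per group: 176 / 0.3 / 0.7 = 838.1, so 838. This agrees.
- Total: 3 × 838 = 2,514. This agrees.

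**Step 3. What is randomised for each contrast.**
- Tailored v random: 838 v 838. At 70% completion, 838 × 0.7 ≈ 587 v 587.
- Emotional regulation v inhibitory control within the RCT: 838 / 2 = 419 v 419, random arm only. At 70% completion, 419 × 0.7 ≈ 293 v 293.
- Of 2 × 838 = 1,676 participants on an active intervention, 838 (50%) receive theirs by algorithm.

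The Study Summary plans 3,600 per cohort. At that size the arms would be 3,600 / 3 = 1,200 and the random-arm split 600 v 600. The half share is unchanged.

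**Step 4. Consistency with the rest of the design.** The Figure 3 caption (section 3.3) says participants in each active arm are analysed together whichever intervention they receive, because the interest lies in how they were allocated. The economic objective fits that; the economic analysis sentence does not. Pooling over allocation method is a live possibility, because the third primary RCT question in section 6.3.2 compares the two interventions in just that way.

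**The case against.** **The analysis section does recognise allocation method.** The RCT part of 6.3.3 opens by saying that allocation method and intervention will each be analysed separately. That is true, but it introduces regression analyses of group differences at T2. The economic paragraph then names only the interventions.

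**The algorithm sentence covers tailoring.** This is the strongest reply, and part of it stands. A natural reading is algorithm-guided delivery, which is close to section 2.1. A reader might infer that the economic objective is left wholly unanswered. The text does not support that, because this sentence leaves room for a tailoring analysis. It still names no arms. Its wording is also ambiguous: section 1.1 ties risk algorithms to the earlier assessment study, whereas section 3.3 allocates by outcome-prediction algorithms from the pilot.

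**Comparators can be left to a later plan.** Detail can. Choosing between two differing Protocol statements of what is compared is more than detail.

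**The economic work may extend to the pilot.** Section 6.3.3 places it within the whole project, and the pilot randomises the two interventions and control 1:1:1 (3,352 / 3 ≈ 1,117 per arm). Table 1 schedules both quality-of-life scales at T0 and T2 for both cohorts. So randomised intervention-level data are not limited to 419 v 419 across the project. But the text sits under the RCT heading, and both statements of the objective belong to the RCT.

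**The bias cannot be sized.** A reader might put a figure on the selection effect. If half the tailored arm went to each intervention, an unadjusted pooled comparison would carry half of whatever prognostic gap separates the two halves: 0.10 to 0.40 SD for assumed gaps of 0.2 to 0.8 SD. The Protocol gives neither the gap nor the split, and does not say that the economic analysis will pool the arms or compare the interventions with each other. Section 6.3.2 plans covariate adjustment for efficacy, which could remove some of the effect if applied here. A gap in outcome SDs is also not a gap in costs or QALYs. The figure is therefore not part of this point.

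**Conclusion.** The mismatch is real. The Study Summary sets a comparison of tailored with random allocation, section 2.1 an evaluation of tailoring without a comparator, and section 6.3.3 an evaluation of the two interventions without a comparator. The softening sentences narrow the gap but do not define the contrast that the objective needs.

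The textual conclusion needs no assumptions. The risk of mixing intervention effect with algorithm selection is conditional: it arises only if an intervention-level economic result pools in the tailored arm. The documents show that half of the RCT's active participants would then be non-randomised to their intervention, but they do not allow the resulting distortion to be quantified.

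This concerns a secondary objective and should be corrected. It does not touch the primary outcome or the sample size.

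**What to change.** Reconcile the Study Summary, section 2.1 and section 6.3.3:

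1. In 6.3.3, state that incremental costs and QALYs are compared between the randomised arms, with tailored v random as the main economic contrast and tailored v control and random v control as further contrasts. Attach the same comparators to the cost per remission.
2. In 2.1, name the comparator for the tailored approach so that it agrees with the Study Summary.
3. In 6.3.3, say which algorithm is meant.
4. If an intervention-level economic result is kept, base it on randomised data only (the RCT's random arm plus control, or the pilot arms) and label it exploratory.

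This is a change of Protocol wording and needs no new data. The price is that the intervention-level result within the RCT is less precise, since it would use about 419 per intervention and not all 1,676 active participants.

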Intervention	
Two 4-week digital self-help preventative interventions have been developed based on two different theoretical underpinnings (emotional regulation and inhibitory control).
 
Pilot study: Participants will be randomly allocated to one of three interventions (emotional regulation; inhibitory control; control condition). The preventative interventions will be stratified into high and low intensity versions and allocated to individuals according to high and low risk of PUI based on a detailed baseline assessment and mobile sensing data.
 
RCT: Participants will receive similar interventions as in the pilot study but allocated in a different way. Participants will be randomised to three separate arms (tailored; random; control), and all will undergo a detailed baseline assessment. For those allocated to the tailored arm, the presence at baseline assessment of risk factors derived from the pilot study will serve as predictors and be used to allocate participants to the intervention (emotional regulation or inhibitory control) most likely to be effective at preventing PUI or reduce problematic behaviour patterns. For those allocated to the random arm, participants will be allocated at random to either of the emotional regulation or inhibitory control interventions.

Follow up duration	
Pilot study: The primary endpoint is the post intervention assessment that takes place at the end of the 4-week intervention phase. The secondary endpoint takes place at 3-months following the primary endpoint. Additional assessments will take place 3-monthly during an optional additional 24-month extension phase.
 
RCT: The primary endpoint takes place at the post intervention assessment at the end of the 4-week intervention phase. The secondary endpoint takes place at 6-months following the primary end point.

Outcomes	
The primary outcome of both the pilot study and the RCT will be PUI measured using the Problematic Internet Use Questionnaire in its short version (PIUQ-SF-9)(Demetrovics et al., 2008).
 
As a secondary outcome, smartphone behaviour will be monitored using mobile sensing giving insights into variables linked to PUI.

1. Introduction

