The research team are currently seeking funding to include an optional extension to Cohort 2. The optional cohort 2 extension will directly follow on immediately from the original 3-month assessment time point and will last a maximum of 28 months to extend data collection until the end of July 2028. Participants who consent to taking part in the extension phase of Cohort 2 will be followed up during this period, receiving push-notifications to complete assessments derived from the same panel as the original phase, every 3 months until the 31-month final endpoint. Additional data will be collected via the Dragon Game app, which includes the cognitive assessment tasks for affect regulation and inhibitory executive control. Should the research team be successful in obtaining funding, a push-notification will appear asking those who consented to take part in the extension to re-confirm their agreement will appear. Should the research team not be successful, a push-notification will appear thanking them for their consent and time but notifying them that this will be the end of their study involvement (see table 3 for an overview of the extension assessments).

Table 1. Schedule of Assessments outcome measures for both interventions and control.

Assessment/Intervention	Baseline T0 (week 0 to week 2)	Intervention (week 2 to week 6)	Post Intervention T1 (week 6)	Monthly ratings (cohort 2 & 3, week 10 & 14) (cohort 3 only, week 18, 22 & 26)	Follow-up Up T2 (Pilot cohort 2: week 18, RCT; week 30,)
Demographics					
Sex	X				
Gender	X				
Age	X				
Year group at school	X				
Mental Health diagnosis	X				
PUI and clinical variables					
S-CIUS*	X		X	X	X
PIUQ	X		X		X
ISAAQ-10 Part B	X		X		X
ISAAQ-ED	X		X		X
ACSID-5	X		X		X
DASS-21	X		X		X
PaedS	X		X		X
SOCS	X		X		X
SDQ	X		X		X
Browser activity	X		X		X
Inhibitory control					
BrainPac SST	X				X
CHI-T	X		X		X
Question on patience	X				X
Emotional regulation					
BrainPac VMAC	X				X
ERQ-CA	X		X		X
Question on mood	X				X
Persons' characteristics					
UPPS-P	X		X		X
Vaccine hesitancy	X				X
Misinformation	X				X
Physical health					
Height and weight	X				X

Favourite Sports interests	X			X
Internet use expectancies, Internet use experiences, FoMO				
IUES	X		X	X
EGS/ECS	X		X	X
SRHI	X		X	X
FoMO	X		X	X
School performance, family background,				
School marks	X			X
Family background	X			X
Socioeconomic status (FAS)				
Mobile sensing⁺				→
Assessment of cost and burden of PUI				
PQ-LES-Q	X			X
EQ-5D-Y	X			X

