Alcohol consumption	X			X
WHODAS 2.0	X		X	X
Ambulatory assessment (AmbA)[#]				
AmbA			X	X

*Note. # Assessed for 7 continuous days. + Continuous recording, -> denotes the period of continuous recording *Collected monthly between T1 and T2, A number of these assessments will also be used during the Intervention (see table 2)*

S-CIUS: Short-Compulsive Internet Use Scale

PIUQ: Problematic Internet Use Questionnaire

ISAAQ-10 Part B: Internet Severity and Activities Addiction Questionnaire - Focus on activities

ISAAQ-ED Internet Severity and Activities Addiction Questionnaire – Eating Disorder

ACSID-5: Assessment of Criteria for Specific Internet-use Disorders

DASS-21: Depression Anxiety Stress Scale

Paeds: Paediatric Self-Stigmatization Scale

BrainPac Stop-Signal-Task (SST)

SOCS: Short Obsessive Compulsive Disorder Screener

SDQ: Strengths and Difficulties Questionnaire

BrainPac- enhanced Value-Modulated Attentional Capture

ERQ-CA: Emotion Regulation Questionnaire for Children and Adolescents

UPPS-P: Urgency – Premeditation - Perseverance - Sensation Seeking - Positive Urgency

CHI-T: Cambridge-Chicago Compulsivity Trait Scale

IUES: Internet Use Expectancies Scale

EGS/ECS: Experience of Gratification Scale and Experience of Compensation Scale

SRHI: Self-Report Habit Index

FoMO: Fear of Missing Out Scale

FAS: Family affluence scale III

PQ-LES-Q: Pediatric Quality of Life Enjoyment and Satisfaction Questionnaire

EQ-5D-Y: European Quality of Life 5 Dimensions

WHODAS 2.0: World Health Organisation Disability Assessment Schedule (adapted for internet use)

Table 2. Schedule of Intervention Assessments and Tasks intrinsic to, for both interventions with high and low PUI.

Assessment/Intervention	Intervention I (4 weeks, weeks 3-6)			
	W3	W4	W5	W6
Both Interventions				
PUI and clinical variables				
S-CIUS		X		
PRISM Internet				
Browser activity	X		X	
Mood-Barometer	X		X	
Self-developed PRISM Internet	X>			
Persons' characteristics				
RR & SER	X			
DBQ-I	X			
Need to belong	X			
UCLA Loneliness Scale	X			
Sofalizing scale	X>			
Internet use expectancies, Internet use experiences, FoMO				
IUES	X>			
FoMO	X>			
FoMO single	X			
Mobile sensing⁺ including App Sessions and Aggregated App usage				
Ambulatory assessment (AmbA)[#]				
AmbA		X>		
Emotional Regulation intervention				
Emotion Memory game		X		
ERQ-CA		X		
Components and functions of emotions video		X		
Pictures with functions of emotions		X		
Emotions and Internet use			X>	

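### In the RCT neither quality-of-life scale behind the QALYs is taken at week 6, the primary endpoint, so incremental QALYs rest on an unmeasured 28-week utility path

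*Protocol*

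**What the plan says.** The Study Summary makes health economics the RCT's secondary objective: "The secondary objective is to evaluate and compare the cost-effectiveness and cost utility of both allocation methods" (tailored and random). Section 6.3.3 then names cost per QALY as one of two headline economic metrics: "We will present the costs of interventions through two primary metrics: incremental costs per QALY gained". The other is cost per adolescent in full remission.

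Two scales are named for quality of life. The PQ-LES-Q "will serve as the primary utility scale". The EQ-5D-Y "will be included as a secondary outcome measure".

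Table 1 in section 3.3, in the block headed "Assessment of cost and burden of PUI", marks both scales at baseline (T0, weeks 0 to 2) and at T2 (week 30 in the RCT), with nothing at T1 (week 6). For the RCT the Study Summary says: "The primary endpoint takes place at the post intervention assessment at the end of the 4-week intervention phase". That assessment is T1.

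Section 6.1.2 adds no quality-of-life rating at T1 or in between. Only the S-CIUS is repeated monthly between T1 and T2. The repeated PQ-LES-Q and EQ-5D-Y ratings in Table 3 belong to the optional extension of the pilot cohort, not to the RCT.

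**The concern.** A QALY gain is a utility difference accumulated over time. The protocol does not spell this out, but it is the standard construction. With values at T0 and T2 only, nothing in the utility data shows what happened during the programme or in the 24 weeks after it. The time at which the trial judges its primary outcome lies inside that gap.

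At stake is the cost-utility half of the RCT's secondary objective. Section 6.3.3 also plans to compare the cost-effectiveness results with those for obsessive-compulsive disorder and gambling disorder. A cost-per-QALY ratio that depends on an unobserved path is a weak basis for that comparison. The RCT's three primary questions are not touched.

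**Working it through.** **Is the empty T1 cell real?** Table 1 is broken by the text extraction, so this was checked against neighbouring rows. On the same part of the table, IUES, EGS/ECS, SRHI and FoMO each carry a separate T1 mark. Within the cost-and-burden block itself, the WHODAS 2.0 row reads "WHODAS 2.0 X X X", that is T0, T1 and T2, while the PQ-LES-Q and EQ-5D-Y rows have two marks each. The gap is in the plan, not in the extraction.

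**Is there a stated figure to reproduce?** No. The protocol gives no utility difference, QALY figure or power calculation for cost utility.

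**Inputs.** From Table 1: baseline ends at week 2, T1 is week 6, T2 is week 30. Assumed, because the protocol gives no trajectory: the between-arm utility difference is 0 at week 2, d at week 6 and r × d at week 30, straight between these points, with the time horizon ending at week 30.

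**Formulas** (in d-weeks; divide by 52 for QALYs):

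- Area with T1 measured: ½ × 4 + ½ × (1 + r) × 24
- Area from T0 and T2 only: ½ × 28 × r
- Share missed: 1 − (two-point area ÷ three-point area)

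| Course after week 6 | r | With T1 | T0 and T2 only | Missed |
|---|---|---|---|---|
| Fully faded by week 30 | 0 | 2 + 12 = 14 | 0 | 100% |
| Half faded | 0.5 | 2 + 18 = 20 | 7 | 65% |
| Sustained | 1 | 2 + 24 = 26 | 14 | 46% |
| Doubles | 2 | 2 + 36 = 38 | 28 | 26% |
| Straight-line growth from week 2 | 7 | 2 + 96 = 98 | 98 | 0% |

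For a fixed incremental cost, cost per QALY would be too high by a factor of 26 ÷ 14 = 1.86 if the effect is sustained and 20 ÷ 7 = 2.86 if it is half faded.

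**Sensitivity to the baseline date.** If the two-point line starts at week 0, its area is ½ × 30 × r. The first three losses become 100%, 62.5% (7.5 against 20) and 42% (15 against 26).

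**Late effect.** If the difference is still 0 at week 6 and reaches E at week 30, the measured-path area is ½ × 24 × E = 12E and the two-point area is ½ × 28 × E = 14E. The two-point estimate is then 14 ÷ 12 = 1.17 times the true area, about 17% too high.

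**The case against.** The strongest reply is that the direction of the error is not known. A reader might infer that the schedule always pulls incremental QALYs toward zero. The protocol does not support that: T1 is the primary endpoint for PIUQ severity, and nothing is said about when quality of life responds. As shown above, later growth shrinks the loss and a purely late effect reverses it. This stands, and the point is worded conditionally for that reason.

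The two-point straight line to week 30 is also an assumption of this check. Section 6.3.3 does not say how QALYs are computed, and its mention of discounting and long-term costs and benefits may imply a longer horizon. With an assumed horizon to week 104 and a sustained effect, the areas would be 2 + 98 = 100 and 14 + 74 = 88 d-weeks, a 12% loss rather than 46%. A fully faded effect would still be missed entirely. This stands too, so the percentages apply to a within-trial analysis.

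A reader might further infer that the week-6 value is beyond any recovery. That goes too far. WHODAS 2.0, DASS-21 and SDQ are collected at T1, and the S-CIUS at T1 and monthly, so utility could be approximated from them. Doing so needs modelling assumptions that the protocol does not state. The planned multiple imputation does not fill the gap by itself, because no participant has an observed utility at T1.

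Nor would adding T1 make the area exact. It does so in the table only because the assumed path bends at T1 and nowhere else.

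The method of computing QALYs may properly be left to an SAP. The visit schedule may not: it is fixed here, and an SAP cannot create measurements.

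**Conclusion.** The point holds in conditional form. In the RCT, utility is unmeasured from baseline to week 30, with the primary endpoint inside that gap.

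If the utility difference is present by week 6 and then holds or fades, a within-trial two-point QALY misses 46% to 100% of the incremental area (42% to 100% if the line starts at week 0). If the difference grows after T1, the loss is smaller or nil. If it arises only after T1, the estimate is about 17% too high. These figures assume straight-line segments and a horizon ending at week 30. The protocol's own data could not show which case applies without an unstated model.

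The finding concerns timing only and is the same whichever scale supplies the utility. Cost per adolescent in full remission is not affected in the same way, because the PIUQ is collected at T1. This should be corrected before RCT data collection starts.

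**What to change.** For all three RCT arms, add to Table 1 at T1 whichever scale supplies the utility. Preferably add both the PQ-LES-Q and the EQ-5D-Y: adding the EQ-5D-Y alone would leave the declared primary utility scale with two time points. State in section 6.3.3 that QALYs are computed by the trapezoidal rule over T0, T1 and T2, adjusted for baseline utility.

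The cost is one or two table rows, one sentence, and one or two extra app questionnaires at an existing assessment. Of the EQ-5D-Y the protocol says: "This short (2-minute) and user-friendly tool offers a visual analogue version". It gives no completion time for the PQ-LES-Q. The burden is a real drawback: T1 already carries 18 marked instruments plus seven days of ambulatory assessment, in 12- to 16-year-olds for whom section 3.4.2 assumes 70% completion.

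If the sponsor decides against the extra questionnaires, section 6.3.3 should at least state how utility between T0 and T2 will be modelled, with sensitivity analyses over different time courses.
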